It is recognized that drug-related hematologic toxicity in this population may be difficult to ascertain given the aggressive hematologic disease and the fact that multiple cycles of therapy may need to be administered for maximal clinical response. Therefore, there will be no dose modifications for hematologic toxicity due to ENTO, decitabine or azacitidine during the first 3 cycles for subjects with active AML. However, after the third cycle of ENTO and decitabine is administered, subjects suspected to have study treatment related ANC and/or platelet count toxicity (ie, fail to recover to at least 50% of the prior cycle's baseline value) will have the dose of decitabine reduced to 20 mg/m²/d on Days 1-9 and the dose of ENTO reduced one dose level. Similarly, after the third cycle of ENTO and azacitidine administration, subjects suspected to have study treatment related ANC and/or platelet count toxicity (ie, fail to recover to at least 50% of the prior cycle's baseline value) will have the dose of azacitidine reduced according to [Table 3-7](#) and the dose of ENTO reduced one dose level. Dose modifications because of concern for drug induced cytopenias prior to Cycle 4 will be discussed with the medical monitor. Dose modifications for hematologic toxicity for subjects who have achieved a CR or CRi are detailed below. For additional safety information, reference the package insert for decitabine and azacitidine.

Table 3-7. Azacitidine Dose Modifications

Nadir Counts		% Dose in the Next Course
ANC (x10⁹/L)	Platelets (x10⁹/L)	
< 0.5	< 25.0	50%
0.5 –1.5	25.0-50.0	67%
> 1.5	> 50.0	100%

Dose Modifications for Hematologic Toxicity for Subjects Who HAVE Achieved < 5% Blasts and Receive Maintenance Therapy With Decitabine or Azacitidine

Subjects who have had a previous dose reduction of decitabine and ENTO and then subsequently have a decrease in blasts to < 5% by morphology, the number of days of decitabine will be reduced to Days 1-4 of each cycle, but the daily dose will remain the same. For example, a subject receiving 20 mg/m²/day on Days 1-9 will move on to receive 20 mg/m²/day on Days 1-4. Subjects will receive the same dose reduction of ENTO. For azacitidine, no dose reduction regimen is necessary.

Neutropenia

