In the event of Grade 4 neutropenia (ANC < 500/μL) that occurs with the second or subsequent cycles of maintenance and persists for 14 days or more or is associated with febrile neutropenia, further cycles of ENTO/decitabine shall be administered once ANC recovers to ≥ 1000/μL with a decrease in the number of days of decitabine and the dose of ENTO will be decreased by 1 dose level (ie, for the first occurrence omit the final day 5 dose of decitabine; for the second occurrence omit the final day 4 dose of decitabine). If there is no evidence of ANC recovery after 14 days, repeat marrow evaluation should be considered. Subjects who require a dose reduction below dose level -1 will not receive ENTO and instead will continue maintenance treatment with decitabine alone. If Grade 4 neutropenia that persists for 14 days or more (or grade 4 neutropenia associated with fever) recurs for the third time, discontinue the ENTO/decitabine. Similarly, in the event of neutropenia that occurs with the second or subsequent cycles of maintenance with azacitidine, and persists for 14 days or more or is associated with febrile neutropenia, the dose of azacitidine will be reduced according to [Table 3-8](#).

Thrombocytopenia

In the event of Grade 4 thrombocytopenia (platelets < 25,000/μL) that occurs with the second or subsequent cycles of maintenance and persists for more than 14 days (or >25,000/μL but requiring prophylactic platelet transfusions to maintain this over the 14 day period), further cycles of ENTO/decitabine shall be administered with a decrease in the number of days of decitabine and the dose of ENTO will be decreased by 1 dose level (ie, for the first occurrence omit the final day 5 dose of decitabine; for the second occurrence omit the final day 4 dose of decitabine). Subjects who require a dose reduction below dose level -1 will not receive ENTO and instead will continue maintenance with decitabine alone. If Grade 4 thrombocytopenia persisting for more than 14 days (or subject requires prophylactic platelet transfusions to maintain >25,000/μL over the 14 day period) recurs for the third time, discontinue the ENTO/decitabine. Similarly, in the event of thrombocytopenia that occurs with the second or subsequent cycles of maintenance with azacitidine, and persists for 14 days or more or is associated with prophylactic platelet transfusions, the dose of azacitidine will be reduced according to [Table 3-8](#).

Table 3-8. Azacitidine Dose Reductions

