WBC or Platelet Nadir % decrease in counts from baseline	Bone Marrow Biopsy Cellularity at Time of Nadir (%)		
	30-60	15-30	<15
	% Dose in the Next Course		
50 - 75	100	50	33
>75	75	50	33

Dose Modifications for Non-hematologic Toxicity for Subjects Who HAVE Achieved CR or CRi and Receive Maintenance Therapy With Decitabine or Azacitidine

Subjects who experience any significant Grade 3 or greater toxicity attributed to decitabine, azacitidine, or ENTO will hold the protocol therapy until it resolves to \leq Grade 2. Then restart ENTO with one dose level reduction and reduce the dose of decitabine to 20 mg/m²/d on Days 1-4 for the first occurrence and decrease the dose of decitabine to 20 mg/m²/d on Days 1-3 for the second occurrence and restart ENTO at the next lower dose. For azacitidine specifically, 50% dose reduction will be applied in combination with ENTO at the next lower dose. Subjects who require a dose reduction below dose level -1 will not receive ENTO and instead will continue maintenance with decitabine or azacitidine alone. If the toxicity recurs for a third time during treatment period, therapy should be discontinued. Decitabine/ENTO or azacitidine/ENTO should not be restarted until the toxicity has resolved to Grade 2 or better. Subjects with controlled Grade 3 infection or febrile neutropenia may continue decitabine or azacitidine in combination with ENTO. If a subject experiences pneumonitis at Grade 4, study treatment must be discontinued but may continue with decitabine or azacitidine alone.

Dose reductions (for either hematologic or non-hematologic toxicity) for subjects with < 5% blasts by morphology may be done twice during the course of maintenance therapy, if necessary.

Group C:

Dose modifications and delays attributed to ENTO for hematologic and non-hematologic toxicities will follow the guidelines in [Appendix 3](#).

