8.9. Sample Size

In Phase 1b, each group will enroll up to 12 subjects, assuming 2 planned dose levels for escalation are tested with up to 6 subjects per level. Assuming 10% of the subjects are unevaluable during dose escalation, up to 14 subjects may be enrolled in each group for a total of up to 42 subjects. In Group B, an additional 6 subjects will be enrolled to evaluate the safety of ENTO in combination with azacitidine prior to the dose expansion.

In Phase 2, approximately 40 additional subjects will be enrolled in Group A. [Table 8-1](#) provides the 90% confidence interval (CI) of 40 subjects for the assumed composite complete remission rate. This sample size ensures a narrow CI (~ 7-14% distance from the point estimates). The composite complete remission rate of standard chemotherapy (7+3) has been reported as 52% in the CALGB study of over 1000 subjects.

Table 8-1. Exact 90% CIs of Composite Complete Remission Rate for a Cohort Size of 40 in Group A

Expected Composite Complete Remission Rate of Entospletinib + 7+3	Exact 90% CI
70%	(56% – 82%)
80%	(67% – 90%)
90%	(79% – 97%)

In the Group B phase 2, approximately 40 additional subjects will be randomized in a 1:1 manner to either treatment arm ENTO + decitabine or ENTO + azacitidine. Randomization will be stratified by age (≤ 75 or > 75 years) and WBC ($\leq 5,000/\mu\text{L}$ or $> 5,000/\mu\text{L}$). Assuming an composite complete remission rate of 50% for both treatment arms, the 90% CI would be 30% to 70% with a sample size of 20. The composite complete remission rate of standard chemotherapy is reported as 20% – 30%. Evaluation between the treatment arms will be based on the totality of clinical data.

Approximately 60 additional subjects will be enrolled in the Group C dose expansion.

A total of 15 initial subjects in Cohort C1A will be evaluated for futility. An additional 15 subjects will be enrolled if greater or equal to 5 (out of 15) CR/CRi are observed. This futility boundary will provide a high chance (84%) of early stopping of the trial if the composite complete remission rate is undesirable (20%) and a low chance (22%) of early stopping if the composite complete remission rate is clinically meaningful (40%). At this time, futility has been met, and thus, Cohort C1A will not move forward.

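### In Group B maintenance, the prolonged-cytopenia rules state an ENTO reduction and a third-occurrence stop with decitabine but neither with azacitidine, so ENTO handling after the same event can depend on the randomised arm

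*Protocol*

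**What the plan says.** Group B Phase 2 randomises subjects 1:1 to ENTO + decitabine or ENTO + azacitidine, with ENTO at 400 mg every 12 hours in both arms (Protocol 3.1.4). On comparing the arms, Protocol 8.9 says: "Evaluation between the treatment arms will be based on the totality of clinical data".

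Protocol 3.3, Group B, has separate paragraphs on neutropenia and thrombocytopenia in maintenance. For decitabine, after a qualifying Grade 4 event, further cycles are given "with a decrease in the number of days of decitabine and the dose of ENTO will be decreased by 1 dose level". If the event "recurs for the third time, discontinue the ENTO/decitabine" is the instruction.

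For azacitidine, the neutropenia sentence begins "Similarly, in the event of neutropenia that occurs with the second or subsequent cycles of maintenance with azacitidine" and ends "or is associated with febrile neutropenia, the dose of azacitidine will be reduced according to" Table 3-8. The thrombocytopenia sentence ends "or is associated with prophylactic platelet transfusions, the dose of azacitidine will be reduced according to" the same table. Neither mentions ENTO.

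Two other rules in the same section do mention it. For haematologic toxicity after the third cycle, the azacitidine sentence adds "and the dose of ENTO reduced one dose level". For non-haematologic toxicity in maintenance, the text reads: "For azacitidine specifically, 50% dose reduction will be applied in combination with ENTO at the next lower dose".

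**The concern.** If sites follow the maintenance paragraphs to the letter, a subject with a prolonged cytopenia has ENTO lowered if randomised to decitabine, and has no stated ENTO action if randomised to azacitidine. ENTO is the investigational drug and is common to both arms. Its dose after toxicity would then vary by arm because of the rule's wording, on top of any difference due to the hypomethylating agent itself.

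Maintenance safety, ENTO exposure, EFS and OS all accrue in this period and fall within the planned descriptive evaluation of the arms. Sites could also reasonably read the azacitidine sentences in different ways, which would add between-site variation in ENTO dosing that nobody intended.

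**Working it through.** **The plan's own figure.** The only sample-size figure for these arms is the exact 90% CI of 30% to 70% for a 50% rate with n = 20 (Protocol 8.9). Clopper-Pearson with 10/20 gives 30.2% to 69.8%, so it reproduces. It concerns remission rates and does not depend on this point; it is useful here only for the arm size.

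**Side by side (Protocol 3.3, second or later maintenance cycle).**

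| Element | Decitabine | Azacitidine |
|---|---|---|
| Neutropenia trigger | Grade 4; 14 days or more, or febrile | No grade; 14 days or more, or febrile |
| Platelet trigger | Grade 4 for more than 14 days, or prophylactic transfusions needed over that period | No grade; 14 days or more, or prophylactic transfusions |
| Hypomethylating agent | Fewer days | Table 3-8 |
| ENTO | Down one level | Not stated |
| Third occurrence | Discontinue ENTO/decitabine | Not stated |
| If ENTO falls below the lowest level | Continue decitabine alone | Not stated |

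The ANC restart count is not treated as a difference. It appears only in the decitabine sentence, but an earlier Group B paragraph lets second and later maintenance cycles be held until ANC reaches 1000 for subjects without evidence of AML, whichever agent they receive.

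**Does the word *similarly* carry the ENTO reduction across?** The post-third-cycle rule also opens its azacitidine sentence with *similarly*, and still spells out the ENTO reduction. The non-haematologic maintenance rule spells it out too, and its fallback covers continuing either agent alone. The maintenance cytopenia paragraphs do neither.

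**Table 3-8.** For a 50–75% fall in counts with 30–60% marrow cellularity, the table gives 100% of the azacitidine dose. Read literally, a subject in that cell has no stated change to either drug after a prolonged cytopenia.

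**Size of the literal difference.** Inputs: ENTO 400 mg, one level down being 200 mg (Table 3-2, assumed to apply in Phase 2). The documents give no event rate, so a fraction f with one event is assumed, equal in both arms.

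- Mean planned dose after the event: decitabine 400(1 − f) + 200f; azacitidine 400. For f = 0.1 to 0.6 this is 380 to 280 mg against 400 mg. If 10 of 20 per arm enter maintenance (assumed), 1 to 6 subjects per arm are affected.
- Over k maintenance cycles: the earliest qualifying event is in cycle 2 and changes later cycles, so at least two cycles are at the unreduced dose. Difference in mean planned dose = 50 × f × (k − 2)/k percentage points.

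| f | k = 4 | k = 12 |
|---|---|---|
| 0.1 | 2.5 | 4.2 |
| 0.3 | 7.5 | 12.5 |
| 0.5 | 12.5 | 20.8 |

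**Would the planned analyses show it?** Protocol 8.6.1 calls for the number and timing of prescribed dose reductions and interruptions. SAP 4.2.1 keeps only the number and percentage of subjects with a reduction, and defines duration regardless of interruptions. SAP 4.2.2 adjusts adherence for prescribed reductions, so a subject correctly on 200 mg and one on 400 mg can both show about 100%. Neither section gives dose intensity or separates dose reductions by treatment phase. SAP 7.7 does not list the dropped timing as a change.

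**A related gap.** The maintenance rules refer to dose level -1. Table 3-2 lists only levels 0 and 1, so the point below which ENTO is stopped is undefined.

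**The case against.** The azacitidine sentences are silent on ENTO; they do not say that it stays at 400 mg. They begin with *similarly*, directly after rules that lower ENTO, so a site could apply the same ENTO step. The two rules that spell out the reduction cover other situations: toxicity after Cycle 3, and non-haematologic toxicity. A difference may even be deliberate, because Protocol 3.3 says that no dose-reduction regimen is needed for azacitidine in previously dose-reduced subjects who then reach under 5% blasts. All of this stands, and it is why the point is an unresolved inconsistency and not a demonstrated error.

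A reader might infer that the randomised arms do not share the same ENTO backbone. The documents do not support that. Starting dose, lead-in, induction dosing, the post-Cycle 3 ENTO reduction and the non-haematologic ENTO reduction match across arms.

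A reader might also infer that a third event leaves 0% of planned ENTO with decitabine and 100% with azacitidine. That does not follow either. The limit of two reductions in maintenance is not arm-specific. The general paragraph opening Protocol 3.3 allows a hold or stop for intolerance, and Protocol 6.4.1 allows discontinuation for unacceptable toxicity.

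The consequence is limited. The arms are whole regimens compared descriptively, with no test specified. The response window closes before maintenance Cycle 1 Day 1 (SAP 6.1.2). Recruitment to Group B Phase 2 closed early (SAP 1), so a protocol edit can reach few subjects, if any. The SAP already reports by arm the exposure duration, maintenance cycles, subjects with a reduction, and adverse events leading to ENTO reduction or interruption. What these leave out is when reductions occurred and how much ENTO was given in maintenance, which is where the arms could diverge.

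**Conclusion.** The inconsistency is real and confined to Group B maintenance from the second cycle onward. On a literal reading, a first prolonged Grade 4 cytopenia halves planned ENTO with decitabine and triggers no stated ENTO action with azacitidine. Whether that was intended cannot be determined from the documents.

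It can affect ENTO exposure and safety in maintenance, and possibly the descriptive comparison of EFS and OS; no effect on EFS or OS has been shown. It cannot affect the primary remission rates at induction completion. The illustrative differences of 2.5 to 20.8 percentage points rest on assumed event rates, the earliest possible event, 4 or 12 maintenance cycles, equal rates in both arms, and the literal reading. It should be corrected, but it is not a flaw in the primary analysis.

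**What to change.** **Protocol 3.3.** Reconcile the azacitidine sentences on maintenance cytopenia with the decitabine rules beside them and with the post-Cycle 3 and non-haematologic rules. For each arm, state the trigger grade and duration, the ENTO action and the recurrence rule, or state that a difference is intended. Reconcile dose level -1 with Table 3-2. Which rule applies is for the sponsor to decide.

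**SAP 4.2.1.** Restore the number and timing of ENTO reductions promised in Protocol 8.6.1. Tabulate them with ENTO dose intensity, by randomised arm, for the ENTO + hypomethylating agent maintenance phase. Read that table alongside any between-arm description of maintenance safety, EFS and OS.

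**Cost.** One clarification, and one table from ENTO administration data already being collected and listed. No added subjects or procedures. The table will have small numbers, since the arms were planned at about 20 each and recruitment stopped short.

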The most common cause of death in both studies was disease progression. Thirty seven deaths have been reported in Study GS-US-339-0102 and 10 deaths have been reported in Study GS-US-339-0103.

Commonly reported AEs and SAEs reported for subjects in Studies GS-US-339-0102 and GS-US-339-0103 are summarized in Sections 4.2.1.3 and 4.2.2.4 of the Investigator's Brochure.

Study GS-US-339-0103 was closed to enrollment because an unacceptable number of subjects developed pneumonitis during the study. In this study subjects received combination treatment with Mono-MSA ENTO and idelalisib. Pneumonitis was reported for 12 subjects (18.2%). Eleven of the 12 pneumonitis cases (91.7%) were SAEs and were \geq Grade 3 in severity: 7 cases were Grade 3, 2 cases were Grade 4, and 2 cases were Grade 5. Five subjects required treatment in the intensive care unit. Due to the unacceptable incidence of pneumonitis, dosing with a combination of Mono-MSA ENTO and idelalisib was discontinued. Subjects were given the option to continue on study for treatment with Mono-MSA ENTO monotherapy after a 14- to 28-day washout period. Of the 8 subjects (12.1%) who continued on with monotherapy, 6 (75.0%) discontinued treatment because of progressive disease.

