3.3. Dosing Delays/Dose Modifications Attributed to Entospletinib (Beyond Cycle 1)

If the following signs or symptoms are medically manageable, they are not to be a consideration with respect to the subject’s dosing or continuation on study: nausea/mild vomiting/diarrhea, drug-related fever or chills, transient and correctable laboratory test abnormalities, line associated thrombosis, or alopecia (see [Appendix 3](#)). Subjects who are intolerant of dose beyond Cycle 1, may either stop study drug (permanent discontinuation) or have a dose hold in consultation with the Medical Monitor if the AE or lab has resolved to Grade 1 or less which may not be re-escalated. If there is loss of disease control during drug interruption which has resolved to Grade 1 or less, subjects may re-start ENTO per the dose modification guidelines below.

Group A:

Subjects experiencing toxicity attributed to any of the study medication during Cycle 1 requiring permanent discontinuation of either drug shall be removed from study. There will be no dose modifications for ENTO for hematologic toxicity during Cycle 1.

Dose modification of ENTO in subsequent cycles is permitted following guidelines provided below. Subjects who experience a non-hematologic toxicity assessed as ENTO related that is Grade 3 or higher will hold dosing of ENTO until the toxicity resolves to Grade 1, and then restart at the next lower dose and continue through the end of the cycle. Missed doses are not to be made up.

Adverse events and laboratory abnormalities will be graded using the CTCAE, Version 4.03.

Dose Modifications for Non-Hematologic Toxicity for Entospletinib and Daunorubicin and Cytarabine and High Dose Cytarabine Maintenance

In subjects who experience flurid heart failure (EF < 45%) or cerebellar toxicity, protocol treatment will be held and no further anthracyclines or cytarabine will be permitted while on the trial. To re-administer and continue with protocol treatment, EF will need to recover to $\geq 45\%$.

If a subject experiences any non-hematologic clinically significant Grade 3 or greater toxicity felt to be related to the combination agents, or high dose cytarabine maintenance, hold the protocol therapy until it resolves to less than Grade 2. Then, if determined related to ENTO, restart ENTO with one dose level reduction. If a subject experiences pneumonitis at Grade 4, study treatment must be discontinued.

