For subjects entering the maintenance phase of treatment, drug related myelosuppression is a greater concern. However, it should again be noted that subjects with continued evidence of AML such as by flow or cytogenetics (even if morphologic blasts are $<$ 5%) should proceed with therapy in a timely way as described above.

For subjects with no evidence of AML, the first cycle of maintenance should proceed on Day 29 as long as marrow cellularity is \geq 10%. However, the second (or subsequent) cycles of maintenance therapy may be held until ANC is greater than or equal to 1000. If there is no evidence of ANC recovery after 14 days, repeat marrow evaluation is needed. If negative for disease and cellularity is \geq 10%, proceed with decitabine and ENTO at decreased doses. Bone marrow evaluation may be done sooner than 14 days at the discretion of the treating physician.

Dose Modifications for Non-Hematologic Toxicity for Entospletinib, Decitabine or Azacitidine

If the subject experiences any non-hematologic clinically significant Grade 3 or greater toxicity felt to be related to either agent during the induction phase beyond DLT assessment, hold the protocol therapy until it resolves to less than Grade 2. Then, if related to ENTO, restart ENTO

with one dose level reduction. If related to decitabine or azacitidine, the respective package insert should be followed for any dose reductions. If institutional guidelines are to be followed, contact the study team for additional guidance. If the toxicity recurs, subject will be removed from study. If protocol therapy is withheld for more than 2 weeks for toxicity related to protocol-based therapy or up to 4 weeks for any other reason, subjects will be removed from protocol. If a subject experiences pneumonitis at Grade 4, study treatment must be discontinued. For additional safety information, reference the package insert for decitabine and azacitidine.

Subjects who have been dose-reduced cannot be returned to a higher dose level.

Toxicities in an individual subject must resolve to less than Grade 2 or to baseline levels before proceeding with the next cycle of treatment.

Dose Modifications for Hematologic Toxicity for Entospletinib, Decitabine or Azacitidine

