Pneumonitis (dyspnea, cough, hypoxia and/or diffuse interstitial pattern or ground-glass opacities on chest CT and no obvious infectious cause)	Maintain current dose level and schedule. Consider Pneumocystis therapy	Withhold dosing until Grade ≤ 1 . Consider systemic corticosteroids and Pneumocystis treatment. May resume at initial or lower dose level at investigator discretion.	Withhold dosing until Grade ≤ 1 . May resume dosing at initial or lower dose level or discontinue dosing at investigator discretion.	Discontinue study treatment
Other Study Drug Related, Non hematological Adverse Events	Maintain current dose level and schedule	Maintain current dose level and schedule	Withhold dosing until Grade < 1 . May resume dosing at initial or lower dose level or discontinue dosing at investigator discretion	Withhold dosing until Grade < 1 . May resume dosing at initial or lower dose level or discontinue dosing at investigator discretion

Appendix 4. Pregnancy Precautions, Definition for Female of Childbearing Potential, and Contraceptive Requirements

1) Definitions

a. Definition of Childbearing Potential

For the purposes of this study, a female born subject is considered of childbearing potential following the initiation of puberty (Tanner stage 2) until becoming post-menopausal, unless permanently sterile or with medically documented ovarian failure.

Women are considered to be in a postmenopausal state when they are ≥ 54 years of age with cessation of previously occurring menses for ≥ 12 months without an alternative cause. In addition, women of any age with amenorrhea of ≥ 12 months may also be considered postmenopausal if their follicle stimulating hormone (FSH) level is in the postmenopausal range and they are not using hormonal contraception or hormonal replacement therapy.

Permanent sterilization includes hysterectomy, bilateral oophorectomy, or bilateral salpingectomy in a female subject of any age.

b. Definition of Male Fertility

For the purposes of this study, a male born subject is considered fertile after the initiation of puberty unless permanently sterile by bilateral orchidectomy or medical documentation.

2) Contraception Requirements for Female Subjects

a. Study Drug Effects on Pregnancy and Hormonal Contraception

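### Group B maintenance: one passage allows restart at Grade 2, another bars the next cycle at Grade 2, and the reach of Appendix 3 is not stated

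*Protocol*

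**What the plan says.** All of the Group B text at issue is in Protocol Section 3.3.

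- **Maintenance, subjects in CR or CRi on decitabine or azacitidine.** "Subjects who experience any significant Grade 3 or greater toxicity attributed to decitabine, azacitidine, or ENTO will hold the protocol therapy" until the event is Grade 2 or lower. The same paragraph repeats the threshold: combined treatment "should not be restarted until the toxicity has resolved to Grade 2 or better". A third occurrence ends therapy. The only pneumonitis rule in the paragraph is for Grade 4.
- **Group B non-hematologic toxicity, general heading.** The first rule is expressly for induction: "hold the protocol therapy until it resolves to less than Grade 2". A later sentence under the same heading carries no phase: "Toxicities in an individual subject must resolve to less than Grade 2 or to baseline levels before proceeding with the next cycle of treatment".
- **Opening paragraph, before the groups divide.** Subjects intolerant of the dose beyond Cycle 1 may stop ENTO or "have a dose hold in consultation with the Medical Monitor if the AE or lab has resolved to Grade 1 or less". It then refers restarts to the guidelines that follow.
- **Appendix 3.** The pneumonitis row withholds ENTO at Grade 2 and at Grade 3 until Grade 1 or lower. For Grade 2 it continues: "Consider systemic corticosteroids and Pneumocystis treatment. May resume at initial or lower dose level at investigator discretion". Section 3.3 directs Group C to follow this appendix. Its title is not limited to any group, and the opening of 3.3 cites it.

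**The concern.** A site managing a Group B subject in maintenance can find two Group B sentences that give opposite answers at the same toxicity grade, and nothing says which one controls. If the event is pneumonitis, the site must also decide whether Appendix 3 applies.

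The first stake is safety: whether a subject with an unresolved Grade 2 event goes back on treatment should not depend on which paragraph was read. The second is the data. The choice of paragraph affects events recorded as leading to ENTO interruption, reduction or discontinuation (SAP 7.1.6.1) and the count of subjects with a dose reduction (SAP 4.2.1). It also affects adherence, which allows for interruptions made under the protocol (SAP 4.2.2), and the deviation category for wrong treatment or dose (SAP 4.3). The same conduct could be compliant under one passage and a deviation under the other.

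**Working it through.** No sample size, error rate or stated figure is involved, so the check sets the thresholds side by side.

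**1. Which rules can apply to a Group B subject in maintenance?**

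| Source | Resume or proceed when | Stated scope |
|---|---|---|
| 3.3, Group B maintenance | Grade 2 or lower (stated twice) | CR/CRi on decitabine or azacitidine maintenance |
| 3.3, Group B next-cycle sentence | below Grade 2, or baseline | Group B, no phase named |
| 3.3, Group B hold rule | below Grade 2 | induction only |
| 3.3, opening | Grade 1 or lower, loosely worded | all groups, beyond Cycle 1 |
| Appendix 3, pneumonitis Grades 2 and 3 | Grade 1 or lower | mandated for Group C; otherwise unstated |

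The induction rule covers a different phase, so its difference from the maintenance rule is not a contradiction. The conflict rests on the first two rows.

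**2. Does the next-cycle sentence reach maintenance?** Its heading names the three drugs and no phase, and the Group B text defines maintenance in 28-day cycles alongside Cycles 1-4. Nothing in the sentence excludes maintenance.

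**3. Where do the two rules disagree?** Take a Grade 3 event that has since improved:

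| Current grade | Baseline grade | Maintenance passage | Next-cycle sentence |
|---|---|---|---|
| 0-1 | any | may restart | may proceed |
| 2 | 2 | may restart | may proceed |
| 2 | 0-1 | may restart | may not proceed |

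They conflict in one cell only: current Grade 2 with baseline Grade 0 or 1.

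**4. Could restart mean within a cycle, so that the rules never meet?** Not reliably. The maintenance passage cuts decitabine to Days 1-4 and then Days 1-3, against Days 1-5 in Table 3-4. A shorter course would ordinarily take effect at the start of a cycle. Even after a mid-cycle restart, a subject still at Grade 2 meets the next-cycle sentence when that cycle ends.

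**5. Pneumonitis.** The maintenance passage is specific only at Grade 4, so a Grade 3 case falls under its general threshold and may restart at Grade 2. If Appendix 3 applies, ENTO stays withheld at Grade 2. If it does not, this second conflict disappears. The documents do not say which.

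**6. Reach into the endpoints.** The Group B DLT window closes 28 days after Cycle 1 Day 1 (Protocol 3.2). Response at induction completion is taken before Day 1 of the first maintenance cycle (SAP 6.1.2). Both precede maintenance.

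**The case against.** The best defense is that the specific rule governs the general one. The maintenance passage has its own heading and states Grade 2 twice, and different phases may properly carry different thresholds. The unphased sentence follows an induction rule and may have been meant for induction. That is a reasonable reading, but the protocol does not state it. It would also leave a gap. Section 3.1.4 offers maintenance to subjects with clinical benefit and allows ENTO alone, whereas the maintenance passage covers CR/CRi on a hypomethylating agent. If the next-cycle sentence stopped at induction, the Group B text would give those other subjects no threshold of its own.

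Three further points on that side stand:

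- The opening of 3.3 is permissive, involves the Medical Monitor and defers to later guidelines. It needs aligning but is not a clean competing threshold.
- Appendix 3 is cited in that opening after a list of manageable events that should not affect dosing, which does not by itself import the appendix's restart rules. A reader might infer a direct contradiction on pneumonitis. The documents support only an unsettled scope.
- A reader might size the problem from the pneumonitis experience in Section 1.2.4, where 12 of 66 subjects (18.2%) were affected and, of those cases, "7 cases were Grade 3, 2 cases were Grade 4, and 2 cases were Grade 5". That study combined ENTO with idelalisib, in CLL and lymphoma, using an earlier formulation. Idelalisib is not used here, so the rate does not carry over to Group B maintenance.

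**Conclusion.** The inconsistency is real but narrow. Within Group B, two passages give incompatible instructions for a maintenance subject in CR or CRi whose non-hematologic event has fallen from Grade 3 or more to Grade 2, when baseline was Grade 0 or 1. This rests on reading the unphased next-cycle sentence as covering maintenance, which its wording allows and nothing rules out. The scope of Appendix 3 for Groups A and B is a separate and weaker ambiguity.

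The number of subjects affected cannot be estimated from the documents. A reader might infer that the main results are at risk. They are not: neither DLTs nor response at induction completion is touched, and the affected outputs are descriptive. SAP Section 1 also reports that Group B Phase 2 recruitment closed early and that the study will be terminated early, so only subjects still on treatment could benefit prospectively. The deviation and dose-change data still need one reference rule. It should be corrected, but it is not a critical defect. No view is taken on which threshold is right.

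**What to change.** In Protocol Section 3.3:

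- Reconcile the Group B next-cycle sentence with the maintenance passage. State whether that sentence applies to maintenance and which passage prevails, and say which rule covers maintenance subjects outside CR/CRi or on ENTO alone.
- Align the opening paragraph with the group text, or cross-refer to it.
- State whether Appendix 3 applies to Groups A and B, including its pneumonitis rows, or only to Group C.

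The sponsor decides which threshold stands. If the protocol is no longer to be amended, record before database finalization which passage was used to classify deviations in Group B maintenance, and report it in the clinical study report.

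The cost is wording only, in an amendment or clarifying letter. No assessments, subjects or analyses are added.
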